3.4.6 Diet

- No calorie-specific diets
- No weight loss medications
- Eat slowly and chew thoroughly
- Stop eating when full

3.4.6.1 POST OP Week 1 and 2
Liquids only moving to full liquids**3.4.6.2 POST OP Week 3 and 4**
Blended diet with puree foods
Do not drink with meals**3.4.6.3 POST OP Weeks 5 and 6**
Soft Diet
Do not drink with meals**3.4.6.4 POST OP Week 7 and beyond**
No texture restrictions
Well balanced low-fat diet
Do not drink with meals
Include high fiber and high protein foods
Three small meals everyday
Drink 8 cups of liquid everyday**3.4.7 Termination**

If a subject decides to withdraw from the study and desires the Lap-Band removed, this will be done using laparoscopic techniques when possible. The appropriate follow-up care will be provided for those cases, including hospital and clinic follow-up when necessary. In these cases, upper gastrointestinal studies will be performed when necessary.

After the five-year study is complete, subjects have the option of having the band surgically removed or keeping the band. If the subject chooses to keep the band, they will be followed with office visits every six months.

3.5 Interim Analysis

After the first 10 patients have completed 6 months of follow-up, an interim analysis of the safety and effectiveness data will be performed and the results submitted to the FDA.

3.6 Adverse Events**3.6.1 Adverse Events**

Peri-operative adverse events include, but are not limited to, nausea and/or vomiting, pneumonia, thromboembolism, obstruction, bleeding, peritonitis, infection, and death.

Post-operative adverse events include, but are not limited to, nausea and/or vomiting, gastric prolapse, band erosion, dysphagia, tubing failure, port migration, esophageal dilation and band explantation.

Potential adverse events related to the Lap-Band® System surgery (per device labeling) include, but are not limited to, the following:

1. Inability to inflate band due to suspected band leak, access port leak, tubing leak, obstruction or other condition
2. Stomach/pouch slippage
3. Erosion
4. Suture disruption
5. Severe infections that require surgical interventions, such as those resulting from gastric perforation, subphrenic abscess, necrotizing fasciitis, pancreatic abscess and any infection that fails to respond to less invasive treatment (culture required)
6. Gastric perforation
7. Splenic injury
8. Hepatic injury
9. Pulmonary emboli
10. Deep vein thrombosis
11. Serious cardiac/respiratory adverse events (i.e. cardiac/respiratory arrest)
12. Adverse events, which in the opinion of a rheumatologist, may be related to the band (i.e. pain, swelling of joints, tightness, redness or swelling of skin, swollen glands or lymph nodes, unusual and unexplained fatigue, and unusual hair loss)
13. Rashes or other skin reactions
14. Pain resulting in hospitalization
15. Any other serious complication that poses a life-threatening condition to the subject
16. Blood loss resulting in a blood transfusion
17. Death

All adverse events will be recorded on appropriate case report form(s). A summary of the adverse events including frequency, type, and severity will be reported.

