2.0 STUDY OBJECTIVES

2.1 Primary Objective

The primary objective of this research is to demonstrate the safety and efficacy of the use of the LAP-BAND® System in the morbidly obese adolescent population in the United States, and therefore provide these individuals with a significantly less morbid and reversible surgical option for weight loss.

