3.2.4 Removal of Subjects from the Trial

A study subject or the parent of the study subject may end their participation in the study at any time. If a subject withdraws, the principal investigator will make reasonable effort to determine the reason for the subjects' withdrawal from the study and complete termination procedures as described in section 3.4.7. Telephone calls, registered letters and offers of transportation to the investigational site are considered reasonable effort.

In addition, the principal investigator may discontinue a patient's participation in the study if the patient fails to comply with the follow-up evaluation schedule (i.e., if patient missed 3 or more sequential follow-up visits.)

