3.4.5 Follow-Up Visits

3.4.5.1 Scheduled Visits

Study data will be collected at 1-2 week, 6 weeks, 3 months, 6 months, 9 months, 12 months, and every 6 months thereafter for a total of five years. Subjects will be weighed and given a physical examination. Parents and subjects will meet with the nutritionist at these same visits.

The subjects will maintain the behavior modification program worked out with the nutritionist and psychologist before surgery. These programs are individualized to each subject's dietary habits, eating habits, and quality of life issues. The subject will be encouraged and counseled to combine their Lap-Band tool with long-term modifications in their lifestyle, including exercise. Weight loss, status of pre-operative comorbidities and development of complications will be reviewed at every follow-up visit. This will include testing to follow pre-operative comorbidities. Baseline laboratory and nutritional parameters will be repeated every 3 months for the first year post op. OGTT will be performed at 1 year and 5 year on the subjects who have impaired glucose tolerance at baseline testing (excluding subjects who have type I or II diabetes who is not clinically safe to perform the test). However, if the HbA1c or fasting blood glucose tests show abnormal results or the subject develops polyuria or polydipsia, additional interval testing should be performed based on ADA guidelines.

All laboratory, gastrointestinal, EKG, nutritional, and psychiatric evaluations which were performed at baseline will be repeated every 12 months.

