3.7.7 Data Collection

Data will be collected by the principal investigator, the nurse practitioner, or nutritionist and documented on a standardized data form. The data will be entered by a research coordinator or the principal investigator in a fashion that maintains patient anonymity, using a unique identification number. The data will be entered into a secure computerized database, which can be accessed only by the principal investigator and the research coordinator with the use of a password. Data collection and statistical analysis will be performed by assigned research personnel, who will access the data using the unique patient identification number assigned.

We will collect relevant life history information from the subject's medical records including illnesses and hospitalizations that occur while subjects are participating in the research, as well as age, ethnic background, marital status, medical history, weight loss, changes in weight-related medical conditions, and information about the surgery and information about lap-band adjustments, and complications. We will collect medical information from physicians and other healthcare providers in General Surgery, Pediatric Surgery, Pediatrics, Psychiatry, and Psychology and from the NYU hospital medical records.

All data will be recorded on case report forms and compared at 6, 12, 24, 36, 48, and 60 months with baseline. Results will be reported descriptively as well as by modeling weight loss in order to assess aggregate outcomes and address the issues of safety and efficacy.

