6.0 Table I

Schedule of Visits and Procedures

Procedure	Screening	PreOP	OP	Visit 1	Visit 2	Visit 3	Visit 4	Visit 5	Visit 6	Visit 7,9,11,13	Visit 8,10,11,14	>18 yrs old (high school graduation)
				Week 1-2	Week 6	3 m	6 m	9 m	1 Y	Every 6m	2 Y, 3Y, 4Y, 5Y	
Informed Consent	X								X		X	
Additional IC for high school grades												X
Inclusion/Exclusion Criteria	X											
Complete Physical Exam	X								X		X	
Demographics Information	X											
Medical History	X											
Wt Loss History	X											
Co-morbidities and Concomitant Medications	X								X	X	X	
Lap-Band Implant/Revision			X									
Lap-Band Adjustment*				X	X	X	X	X	X	X	X	
Follow up Clinical Assessment				X	X	X	X	X	X	X	X	
Labs												
Metabolic Panel		X				X	X	X	X		X	
Hematology Panel		X				X	X	X	X		X	
Thyroid Panel		X				X	X	X	X		X	
Lipid Panel		X				X	X	X	X		X	
Hepatic Function Panel		X				X	X	X	X		X	
Nutritional Panel		X				X	X	X	X		X	
HbA1c & Insulin		X				X	X	X	X		X	
OGTT*		X							*X		*X	
Urinalysis		X							X		X	
Serum Pregnancy Test (If female)		X							X		X	
EKG		X							X		X	
Pulmonary Function Test (If indicated)		X							X		X	
Chest X-Ray		X										
Gall bladder ultrasound		X										
Bone Density		X										
Gastrointestinal Evaluation												
Esophagram		X							X		X	
Esophageal manometry (if necessary)		X							X		X	
Sleep Apnea Test (if indicated)		X							X		X	
Psychiatric Evaluation												
Psychiatric Assessment*	X					*X	*X		X		X	
Child Depression Inventory	X								X		X	
Three-Factor Eating Questionnaire	X								X		X	

Child Behavior Checklist	X								X		X	
Youth Evaluation Scale	X								X		X	
SF-36 Health Survey	X								X		X	
Nutritional Evaluation												
Initial Nutritional Assessment	X											
Follow up Nutritional Assessment		X	X	X	X	X	X	X	X	X	X	
Adverse Event Evaluation		X	X	X	X	X	X	X	X	X	X	

*OGTT will be performed at 1 year and 5 year on the subjects who have impaired glucose tolerance at baseline testing (excluding subjects who have type I or II diabetes wh is not clinically safe to perform the test). However, if the HbA1c or fasting blood glucose test show abnormal results or the subject develops polyuria or polydipisa, additional testing should be performed based on ADA guidelines.

*Additional follow up psychiatric assessment will be performed at 3 months and 6 months for the patients with antidepressants and moderate to severe psychiatric history.

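### Five-year device complications have no time-based estimate, interval or rule for incomplete follow-up, although safety is part of the primary objective; the resulting bias matters mainly for a composite, for common events or at high loss

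*Combined protocol and SAP*

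**What the plan says.** Section 2.1 makes safety and efficacy joint aims: "The primary objective of this research is to demonstrate the safety and efficacy". It goes on to present the band as a less morbid option. Sections 3.1 and 3.3 set five years of follow-up for up to 120 implanted subjects.

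Section 3.6.1 lists gastric prolapse, erosion, tubing failure, port migration, esophageal dilation and explantation among the post-operative events. Its reporting rule is one sentence: "A summary of the adverse events including frequency, type, and severity will be reported".

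Ascertainment during participation is well provided for. Section 3.4.5.1 says "development of complications will be reviewed at every follow-up visit", Table I has a row for "Adverse Event Evaluation" at every visit, and section 3.7.7 adds outside sources: "We will collect medical information from physicians and other healthcare providers".

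Section 3.2.4 lets families withdraw at any time and lets the investigator discontinue a subject "if patient missed 3 or more sequential follow-up visits". The contact efforts in that section ("Telephone calls, registered letters and offers of transportation to the investigational site are considered reasonable effort") serve to learn why a subject withdrew and to complete termination procedures. Section 3.4.7 deals with one exit route ("If a subject decides to withdraw from the study and desires the Lap-Band removed") and with office visits after year five.

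**The concern.** The complication rate is the main evidence for the safety half of the primary objective. Band complications can appear at any time while the device is in place, so a five-year risk is meaningful only with a stated time origin, a denominator and a rule for subjects whose observation stops early. The plan gives none of these.

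If a subject leaves with the band in place and later complications are not captured, that subject still counts in the denominator of a crude frequency as though event-free. The reported rate is then too low, which favours the device. Without an interval, a reader also cannot see how little 120 subjects can exclude.

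**Working it through.** **1. Is there an estimator elsewhere?**
- 3.5: an interim safety and effectiveness analysis after 10 subjects reach six months. No five-year estimate.
- 3.7.5: 30-day mortality, annual esophagrams, nutritional monitoring. No estimator or interval for device complications.
- 3.7.6: models or tests for % EWL, BMI, comorbidities, SF-36 and depression. Nothing for adverse events.
- 3.7.7: data compared with baseline at fixed months and reported descriptively; only weight loss is modelled. A complication that can arise only after implantation has no baseline value.
- 3.7.8 and 3.7.10: stopping rules stated as event counts, and DSMB and safety-monitor review. These govern conduct and do not define the reported risk.

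**2. Is safety follow-up required after early exit?** No section in the file requires it for a subject discontinued early with the band in place. Section 3.7.7 limits the collection of illnesses and hospitalizations to the period of participation.

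**3. Size.** The plan has no figure to reproduce: it states no complication rate, loss rate or safety precision target. N = 120 is from section 3.1. Assumed: true five-year risk F, five-year loss D, constant hazards, loss independent of risk, no events captured after loss.

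- Hazards: he = −ln(1−F)/5 and hd = −ln(1−D)/5.
- Expected crude frequency over all implanted: C = he/(he+hd) × [1 − (1−F)(1−D)].
- Example, F = 0.10 and D = 0.30: he = 0.02107, hd = 0.07133, so C = 0.2280 × (1 − 0.63) = 0.0844.
- Coverage: the probability, with X binomial(120, C), that the exact (Clopper-Pearson) 95% interval for X/120 contains F. For F = 0.10 this means X from 6 to 19; for F = 0.20, X from 16 to 33.

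Expected crude frequency, with coverage in brackets:

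| True risk | 20% loss | 30% loss | 40% loss |
|---|---|---|---|
| 5% | 4.5% (96.5%) | 4.2% (95.9%) | 3.9% (94.9%) |
| 10% | 9.0% (95.9%) | 8.4% (94.3%) | 7.9% (91.6%) |
| 20% | 18.0% (92.7%) | 16.9% (88.1%) | 15.8% (80.5%) |
| 30% | 27.1% (92.4%) | 25.5% (85.7%) | 23.8% (74.4%) |

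The relative shortfall hardly depends on the risk: about 10% at 20% loss and about 21% at 40% loss. Set against sampling error, it matters more as the risk rises. With complete follow-up the exact intervals would be 1.9 to 10.6% for 6/120, 5.3 to 16.8% for 12/120 and 13.3 to 28.3% for 24/120.

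**4. Does censoring repair it?** In simulation (N = 120, 4,000 runs per setting), Kaplan-Meier at 40% loss averaged 10.1, 20.0 and 30.0% for true risks of 10, 20 and 30%, with log-log interval coverage of about 95 to 96%. At 20% risk and 30% loss (20,000 runs) the mean interval width was 15.8 points, against 14.1 for the crude interval.

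**5. If loss is related to risk.** With hazard k × he after loss, the true risk is 1 − [exp(−5(he+hd)) + ∫₀⁵ hd·exp(−(he+hd)t)·exp(−k·he·(5−t)) dt]. For he set at F = 0.20 and D = 0.30, it is 22.6% when k = 2 and 18.5% when k = 0.5, while a censored estimate still gives 20.0%. Censoring alone therefore needs a sensitivity analysis.

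**The case against.** **The size is assumed, and most single complications are probably uncommon.** This stands. At 10% risk or below and up to 30% loss, coverage stays close to nominal and the bias is at most 1.6 points. For esophageal dilation the higher risks are hard to apply to a trial that runs to completion. Section 3.7.8 ends the trial if two or more of the first 25 develop it, and with full follow-up that has probability 1 − (1−p)^25 − 25p(1−p)^24, or 73% at p = 0.10 and 97% at p = 0.20. A reader might infer that every reported rate would be seriously misleading; the calculations do not support that.

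**Descriptive adverse event tables are normal in a single-arm study, and the plan sets no safety hypothesis or threshold.** True, and none is asked for. A descriptive five-year rate still needs a denominator, a follow-up time and an interval when safety is a primary aim.

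**The plan has other safety provisions.** The interim analysis, stopping rules, DSMB and independent surgeon are real safeguards, but none yields a five-year estimate.

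**Two further inferences go too far.** A reader might say the same data could be reported as about 17% (20/120) or 23% (20/88, events over events plus event-free completers). No section mentions the second denominator, and restricting numerator and denominator alike to subjects not lost gives F(1−D)/(1−D) = F, unbiased under independent loss. A reader might also conclude that complications are poorly captured in general. During participation they are not; the gap is after exit. Discontinuation for missed visits is discretionary, and its share of any loss is unknown.

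**Explantation is not always morbidity.** This stands. Section 1.1 presents the band as removable after sufficient weight loss, and section 3.4.7 offers removal at withdrawal, so one explantation curve would mix elective and complication-driven removals.

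**Conclusion.** The specification gap is established from the text and needs no assumed rate: the plan defines no time-based estimate, interval or handling of incomplete follow-up for device complications, and nothing in the file requires safety data after early exit. The direction follows if lost subjects stay in the denominator and their later events go uncaptured: a crude frequency understates five-year risk.

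The size is conditional on assumed constant hazards and independent loss. It is small for rare single components. It becomes material for a composite or common events (88.1% coverage at 20% risk and 30% loss) or at high loss (91.6% at 10% risk and 40% loss). Consent terms and case report forms were not seen, so provisions there for later contact or event dates cannot be excluded. This is an inexpensive improvement that should be made; it does not show that the trial's safety results would be invalid.

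**What to change.** **Analysis (sections 3.6.1 and 3.7.5).** For all implanted subjects, report cumulative incidence at 1, 3 and 5 years from implantation, with 95% confidence intervals and numbers at risk:
- for a composite of any device complication, and for prolapse or slippage, erosion, port or tubing failure, esophageal dilation and explantation;
- censoring at last contact, with explantation or death as competing events where relevant;
- with complication-driven and elective explantation shown separately as well as together;
- with follow-up time stated, and one simple sensitivity analysis for risk-related loss on the composite, such as halving and doubling the hazard after loss.

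Record onset or detection dates for all device events. Serious event reports under section 3.6.3 already carry implantation and event dates, so this mainly means checking non-serious events.

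**Follow-up (sections 3.2.4 and 3.7.7).** State that discontinuation for missed visits ends scheduled study visits only, and that adverse events and band status continue to be sought by telephone and from medical records to five years unless consent or assent is withdrawn.

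**Cost.** Analysis wording, a check of date fields, a short amendment, and some extra calls and chart review. Reported rates may be less favourable and their intervals wider.

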3.6.2 Adverse Event Recording

Adverse events are intended to be volunteered by subjects or observed by the investigator. All adverse events are to be recorded on appropriate case report forms. The investigator is instructed to report any serious adverse event immediately to the IBRA.

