3.4.5.2 Band Adjustments

Fluid will be added to or removed from the band as indicated by the clinical progress, physical examination, and esophagram done at follow-up visit.

The adjustments will be performed as per study device manufacture's DFU.

Visits for band adjustments can also be initiated by the patient or their course between scheduled visits. If they lose weight too quickly; develop symptoms such as heartburn, nausea, vomiting or overeating; or develop a condition or illness requiring them to eat more, they will be evaluated for removal of fluid from the band. If they lose weight too slowly or overeat, they will be evaluated for addition of fluid to the band. Each evaluation will involve review of their clinical progress, physical examination, and esophagram if necessary.

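### Section 3.6.2 describes passive adverse event reporting and no section says how symptoms are elicited at visits, so nausea, vomiting and dysphagia risk being under-counted

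*Combined protocol and SAP*

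**What the plan says.** Safety is half of the primary objective in section 2.1: "The primary objective of this research is to demonstrate the safety and efficacy of the use of the LAP-BAND® System". The safety output promised in section 3.6.1 is descriptive: "A summary of the adverse events including frequency, type, and severity will be reported".

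Section 3.6.2 is the only place that states how an event reaches the record: "Adverse events are intended to be volunteered by subjects or observed by the investigator".

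Other sections say when events are looked at:

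- Section 3.4.5.1: "Weight loss, status of pre-operative comorbidities and development of complications will be reviewed at every follow-up visit", and at these visits "Subjects will be weighed and given a physical examination".
- Table I has an "Adverse Event Evaluation" row, marked before surgery, at surgery and in every post-operative visit column.
- Section 3.4.5.2: subjects who develop heartburn, nausea or vomiting, among other triggers, are told that "they will be evaluated for removal of fluid from the band".
- Section 3.7.5 schedules annual esophagrams, and blood work for nutritional deficiency.
- Section 3.7.7 collects illnesses, hospitalizations and complications from medical records and other providers.

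No section gives a standard adverse event question or a symptom checklist.

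**The concern.** Section 3.6.1 names nausea, vomiting and dysphagia as adverse events. Unless they are severe enough to lead to care or a visible finding, these exist in the data only if the subject mentions them. Section 3.6.2 sets a passive rule. The visit reviews elsewhere do not replace it, so staff could complete the Table I row by recording only what was volunteered or seen, or by questioning the subject systematically. Both practices fit the text, and they would give different frequencies.

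The direction of any error is what matters. There is no concurrent control group to share the same under-ascertainment, so a low count reads as a safer device. The safety data go to the FDA in the interim report (3.5) and to the DSMB at its quarterly meetings (3.7.10). An undefined method of elicitation also makes the frequencies hard to set beside those of other series.

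**Working it through.** The plan states no figure on this point, so there is none to reproduce. The check is a comparison of sections, followed by an illustration on assumed values.

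**1. When and how.** Section 3.4.5.1 gives six visits through month 12 (1-2 weeks, 6 weeks, 3, 6, 9 and 12 months), then one every 6 months from month 18 to month 60, which is eight more: 6 + 8 = 14. The Table I row carries 10 marks: 2 (before and at surgery) + 6 (visits to 1 year) + 2 (the two columns for later visits). Every post-operative visit is therefore covered as to timing. As to method, the section says only that complications are reviewed, and the Table I row has no footnote. Section 3.6.2 alone describes a method.

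**2. What each route can find.**

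| Route | Finds | Does not reliably find |
|---|---|---|
| Physical examination (3.4.5.1) | Signs present on the day | Intermittent nausea, vomiting, dysphagia |
| Annual esophagram (3.7.5) | Esophageal anatomy, band position | Symptoms without an anatomical change |
| Blood work (3.7.3, 3.7.5) | Nutritional deficiency | Symptoms |
| Medical records (3.7.7) | Events that led to care | Symptoms for which no care was sought |
| Band-adjustment evaluation (3.4.5.2) | Symptoms that are reported | Symptoms that are not mentioned |

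What remains is nausea, vomiting and dysphagia that the subject does not raise. Pain does not belong on this list: 3.6.1 limits it to pain resulting in hospitalization and pain that a rheumatologist considers possibly band-related.

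**3. Size, on assumptions only.** Let N = 120 (section 3.1), p = the true proportion of subjects with the symptom, and c = the probability that an affected subject is recorded. Then recorded subjects = N × p × c. Neither p nor c is in the documents.

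| Assumed p | True subjects | Recorded if c = 0.8 | Recorded if c = 0.5 |
|---|---|---|---|
| 10% | 12 | 9.6 | 6 |
| 20% | 24 | 19.2 | 12 |
| 30% | 36 | 28.8 | 18 |

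At p = 20%, 12 of 120 recorded (10%) has an exact 95% interval of 5.3% to 16.8%, which misses 20%. With 19 of 120 recorded, the interval is 9.8% to 23.6%, which includes it.

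c must apply to subjects. If each episode has a 0.5 chance of capture, independently, a subject with two episodes is recorded with probability 1 − 0.5² = 0.75 (18 of 24), and one with three episodes with probability 1 − 0.5³ = 0.875 (21 of 24). Recurrent symptoms therefore lose less than the 0.5 column suggests.

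**4. Stopping rules.** Section 3.7.8 uses surgical deaths, esophageal dilation in the first 25 patients and nutritional deficiency in the first 35. The last two rest mainly on scheduled imaging and laboratory tests, so passive symptom reporting affects them little.

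**The case against.** The strongest reply is that observation by the investigator is scheduled. There are 14 post-operative visits with an examination and a review of complications, an adverse event row at each, a meeting with the nutritionist for subject and parents (where vomiting or difficulty swallowing bears directly on eating), yearly esophagrams and a records search. Section 3.7.2 also follows reflux through symptoms or esophagram. The case report forms are not among the documents and may already contain prompts. The adverse event output is descriptive, with no threshold rate or test to distort.

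Most of this stands. A reader might infer from 3.6.2 that events are captured only when volunteered or noticed by chance. The documents do not support that, because review at each visit is required.

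A reader might also infer from 3.4.5.2 that adolescents will hide symptoms to avoid losing fluid from the band. That is a possible motive, not something the documents show. A subject who is vomiting also has reason to seek relief, and patients may initiate visits between the scheduled ones, which softens the argument from six-month recall.

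What the reply does not supply is a method. Scheduling a review does not say what is asked, and the only sentence that addresses the question points to passive capture.

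**Conclusion.** The point holds as a gap and an inconsistency in the safety ascertainment rule: 3.6.2 is passive, while 3.4.5.1 and Table I require a review at each visit without saying how symptoms are elicited. The consequence is a risk of under-counting confined to nausea, vomiting and dysphagia that no other route detects, in a direction that would favour the device.

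A reader might go further and conclude that these events are in fact under-counted, or that the reported interval would exclude the true rate. The documents support neither. The true rate and the capture rate are both assumptions, and at 80% capture the interval in the illustration still contains the assumed 20%. The conclusion rests on 3.6.2 being followed literally and on the case report forms not already prompting for symptoms. This is a low-cost improvement.

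**What to change.** Replace the first sentence of 3.6.2 with a rule such as:

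> At every scheduled and band-adjustment visit, the subject (and the parent, while the subject is a minor) is asked one open, non-leading question about health since the last visit, and then a short fixed list of symptoms: nausea, vomiting, dysphagia and heartburn. Events that are volunteered or observed are also recorded. The case report form states whether each event was elicited or spontaneous.

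Heartburn is on the list because 3.4.5.2 names it, although 3.6.1 does not. The list should hold only what a patient can report. The full 3.6.1 list includes items such as splenic injury and suture disruption, which are not suitable as questions to a subject.

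In the adverse event summary, tabulate elicited and spontaneous events separately, so that the spontaneous counts remain available for comparison with series that did not prompt. Add a cross-reference to this rule in 3.4.5.1 and at the Table I row.

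The cost is a short addition to the case report form and a few minutes at existing visits, with no added visit, test or change to clinical management. The downside is a higher reported rate of minor events, which the separate tabulation makes interpretable.
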